7.1.2. Adverse Events

Assessment of AEs will include the type, incidence, severity (graded by NCI CTCAE version 4.03) timing, seriousness, and relatedness.

Adverse events that occur during the study, after the patient receives the first dose, will be recorded on the AE CRF page.

7.1.3. Laboratory Safety Assessment

Hematology and blood chemistry will be drawn at the time points described in the [Schedule Of Activities](#) and analyzed at local laboratories.

Hepatitis B surface antigen (HBsAg), hepatitis B core antibody (HBcAb), hepatitis C antibody (HCV Ab), and HIV serology testing should be conducted at screening. Other tests may be conducted per standard practice to confirm an active hepatitis or HIV infection.

All laboratory safety assessments conducted on Cycle 1 Day 1 (C1D1) must be completed prior to dosing. If baseline assessments are performed within 72 hours prior to C1D1, there is no need to repeat assessments on C1D1. Assessments performed on Cycle 2 Day 1 (C2D1) and each subsequent cycle should be performed within 48 hours prior to dosing. Investigators may have additional blood tests performed for the purpose of planning treatment administration, dose modification, or following AEs. Day 1 safety laboratory test results need to be reviewed by the investigator prior to dosing at the beginning of each cycle for dosing confirmation and administration rate.

In addition, a serum sample will be collected at pre-dose C1D1. This sample will be utilized as a baseline sample for cytokine measurement should cytokine release syndrome occur. Optional samples for cytokine analysis will be collected throughout the study, as clinically indicated.

Table 4. Laboratory Tests

Hematology	Chemistry	Coagulation	Serology	Immunology	Urinalysis ^a	Pregnancy Test or Postmeno-pausal Status
Hematocrit	ALT	INR/PT	HBsAg, HBcAb ^b	CRP or HsCRP (Part 1 only)	Urine dipstick for urine protein: If positive, collect a spot urine to calculate UPCR or collect 24-hr and microscopic (Reflex Testing).	For female patients of childbearing potential, serum or urine test (sensitivity ≥ 25 mIU/mL); For female postmenopausal patients who have not experienced their menses for at least 12 consecutive months. Serum FSH test at screening only, to confirm post menopause.
Hemoglobin	AST	aPTT or PTT	HCV Ab ^b	TBNK (whole blood, Part 1 only)		
	lactate dehydrogenase (LDH)		HIV serology	Cytokine		
Platelets	Alkaline Phosphatase					
WBC	Sodium					
Absolute Neutrophils	Potassium					
Lymphocytes	Magnesium					
Monocytes	Chloride					
Eosinophils	Total Calcium					
Basophils	Total Bilirubin ^c					
CBC	BUN or Urea				Urine dipstick for urine blood: If positive twice or as clinically indicated perform microscopic analysis (Reflex Testing).	
	Creatinine					
	Uric Acid					
	Glucose (non-fasted)					
	Albumin					
	Phosphorous or Phosphate					
	Lipase					
	Amylase					
	TSH + reflex free T4 and free T3					

ALT = alanine aminotransferase; aPTT = activated partial thromboplastin time; AST = aspartate aminotransferase; BUN = blood urea nitrogen; CBC = complete blood count; CRP = C-reactive protein; HBsAg = hepatitis B antigen; FSH = follicle stimulating hormone; HBcAb = hepatitis B core antibody; HCV = hepatitis C virus; HIV = human immunodeficiency virus; HPV = human papilloma virus; HsCRP = high sensitivity C-reactive protein; INR = international normalized ratio; partial thromboplastin time = PTT; T3 = triiodothyronine; T4 = thyroxine; TBNK = T cell/B cell/natural killer cell; TSH = thyroid stimulating hormone; UPCR = urine protein to creatinine ratio; WBC = white blood cells;

- Dipstick is acceptable to perform urinalysis. Microscopic analyses if clinically indicated (eg, only after the second positive dipstick result for heme). If $\geq 2+$ protein on urine dipstick, then collect spot urine sample to calculate UPCR or collect 24hr urine.
- In the case of apparent ongoing HBV or HCV infection, reflex serum viral load testing will be performed.
- For potential Hy's Law cases, in addition to repeating AST and ALT, laboratory tests should include albumin, creatine kinase, total bilirubin, direct and indirect bilirubin, gamma glutamyl transferase, prothrombin time (PT)/INR, alkaline phosphatase, total bile acids, and acetaminophen drug and/or protein adduct levels.

7.1.4. Vital Signs and Physical Examination

Patients will have a physical examination to include weight, vital signs (temperature, sitting BP, sitting pulse rate after 5 minutes of rest, and pulse oximetry at rest and after exertion), assessment of ECOG performance status and height (height will be measured at screening only).

See [Schedule Of Activities](#). Abbreviated PEs should be performed as appropriate at each visit where complete PEs are not required.

7.1.5. (12-Lead) Electrocardiogram

Electrocardiogram machines to be utilized in this study will be supplied by a third party vendor.

At screening, a single 12-lead ECG tracing (with a 10-second rhythm strip) will be obtained. For Cycle 1 Day 1 and all subsequent specified time points (see [Schedule Of Activities](#)), triplicate 12-lead ECG tracings (with a 10-second rhythm strip) will be obtained.

Generally, baseline and all corresponding time point ECGs should not be collected within 3 hours after food or beverage consumption and should be performed after the patient has rested quietly for at least 10 minutes in a supine position. All 12 lead ECGs should be confirmed by a qualified person at the institution and will be reviewed by a central laboratory. ECGs on Day 1 of each cycle will be collected prior to dosing, and at the end of infusion or SC injection (approximately 1 hour) following administration of each dose of PF 06801591. When the timing of these measurements coincides with a blood collection, the ECG should be obtained prior to the nominal time of the blood collection, BP, and pulse rate.

When matched with PK sampling, the ECG should preferably be carried out before each PK sample drawing such that the PK sample is collected at the nominal time (ie, the timing of the PK collections overrides the timing of the ECG collections).

At each time point (see the [Schedule Of Activities](#) and ECG manual), 3 consecutive ECGs will be performed at approximately 2 minutes apart to determine the mean QTcF interval; the average of the triplicate ECG measurements collected at each pretreatment time point on Day 1 of each cycle will serve as each patient's time-controlled baseline QTc value. If the mean QTcF is prolonged (≥ 45 msec from the pre-dose baseline or is ≥ 500 msec), then the ECGs should be re-evaluated by a qualified person at the site for confirmation as soon as the finding is made, including verification that the machine reading is accurate. If manual reading verifies a QTcF of ≥ 45 msec from the pre-dose baseline or is ≥ 500 msec, immediate correction for reversible causes (including electrolyte abnormalities, hypoxia and concomitant medications for drugs with the potential to prolong the QTcF interval) should be performed. In addition, repeat ECGs should be immediately performed hourly for at least 3 hours until the QTcF interval falls below ≥ 45 msec from the pre-dose baseline or is ≤ 500 msec depending on the type of change originally observed. If QTcF interval reverts to less than 45 msec from the pre-dose baseline or is ≤ 500 msec, and in the judgment of the

investigator(s) and sponsor is determined to be due to cause(s) other than investigational product, treatment may be continued with regular ECG monitoring. If in that timeframe the QTcF intervals rise above ≥ 45 msec from the pre-dose baseline or is ≥ 500 msec the investigational product will be held until the QTcF interval decreases to ≤ 45 msec from the pre-dose baseline or is ≤ 500 msec, depending on the type of change originally observed.

Note: If QTc values remain ≥ 500 msec (or ≥ 45 msec from the pre-dose baseline) for greater than 4 hours (or earlier at the discretion of the investigator); or QTc intervals get progressively longer, the patient should undergo continuous ECG monitoring. A cardiologist should be consulted if QTc intervals do not return to less than 500 msec (or to < 45 msec above the pre-dose baseline) after 8 hours of monitoring (or earlier at the discretion of the investigator).

Once the QTcF interval decreases to ≤ 45 msec from the pre-dose baseline or ≤ 500 msec, depending on the type of change originally observed, patients may restart the investigational product at the next lowest dose level. If the QTcF interval has still not decreased to ≤ 45 msec from the pre-dose baseline or ≤ 500 msec after 2 weeks (depending on the type of change originally observed), or if at any time a patient has a QTcF interval > 515 msec or becomes symptomatic, the patient will be removed from the study. Additional triplicate ECGs may be performed as clinically indicated.

Prior to concluding that an episode of QTcF interval prolongation is due to investigational product, thorough consideration should be given to potential precipitating factors (eg, change in patient clinical condition, effect of concurrent medication, electrolyte disturbance) and possible evaluation by specialist.

If patient experiences a cardiac or neurologic AE (specifically syncope, dizziness, seizures, or stroke), triplicate ECGs should be obtained at the time of the event.

In some cases, it may be appropriate to repeat abnormal ECGs to rule out improper lead placement as contributing to the ECG abnormality. It is important that leads are placed in the same positions each time in order to achieve precise ECG recordings. If a machine-read QTc value is prolonged, as defined above, repeat measurements may not be necessary if a qualified physician's interpretation determines that the QTc values are in the acceptable range.

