- z. **Contraceptive Check (frequency to match that of pregnancy tests):** Male patients who are able to father children and female patients who are of childbearing potential will need to affirm that they meet the criteria for correct use of 2 of the selected methods of contraception throughout the study and continue for at least 5 months after the last dose. The investigator or his or her designee will discuss with the patient the need to use 2 highly effective contraception methods consistently and correctly and document such conversation in the patient's chart. In addition, the investigator or his or her designee will instruct the patient to call immediately if one or both selected contraception methods are discontinued, or if pregnancy is known or suspected in the patient or the patient's partner.
- aa. **Subsequent Cycles:** For Blood PK samples for PF-06801591 and for PD-1 Receptor Occupancy samples (whole blood) refer to the separate PK & Pharmacodynamic [Schedule of Activities](#).
- bb. **End-of-Treatment Visit:** conducted at the visit that the patient is discontinued from the trial and no longer than 1 week after the patient has been discontinued. Complete tumor assessments if not completed in the last 8 weeks.
- cc. **1-Month and Late irAE Follow-up:** At least 28 days and no more than 35 days after discontinuation of treatment or last dose of study drug whichever is later, patients will return to undergo review of concomitant medications, vital signs, and assessment for resolution of any treatment-related toxicity. Patients continuing to experience toxicity at this point following discontinuation of treatment will continue to be followed at least every 4 weeks until resolution or determination, in the clinical judgment of the Investigator, that no further improvement is expected. To collect additional late immune-related AE information, all patients will have a follow-up phone call 90 and 120 days (± 7 days) after last dose administration date to collect post-treatment related AE information. If any concern arises, the patient will be called in for an inpatient

follow-up visit within 5 calendar days of the initial phone call (assessments will be the same as the assessments performed 28 days (range 28-35 days) after EOT follow-up visit).

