5.4.3.1. Rules For Dose Delay/Interruption/Discontinuation

Events including, but not limited to, pneumonitis, colitis, creatinine, and liver function test (LFT) elevation should be monitored carefully with this class of agents. To facilitate the early recognition and prompt intervention in the event of clinically AEs related to study treatment, management algorithms have been developed for suspected pulmonary, gastrointestinal, liver, endocrine, skin, cardiac, renal, or other immune-related toxicities (See [Appendix 8](#)). For non-irAEs, please refer to the rules for dose delay/interruption/discontinuation below:

- Withhold treatment for: creatinine, AST, ALT, or total bilirubin for drug-related Grade 2 elevations except if they were >ULN at baseline.
- Withhold treatment for any other Grade 3 drug-related AEs.
- Resume treatment when drug-related AE recovers to Grade 0-1 except when creatinine, AST, ALT, or total bilirubin were >ULN at baseline.
- Discontinue treatment for drug-related Grade 3-4 creatinine, AST, ALT, or total bilirubin elevations except if they were >ULN at baseline.
- Discontinue treatment for any other Grade 4 drug-related AEs or laboratory abnormality, except for the following events which do not require discontinuation:
 - Isolated Grade 4 amylase or lipase abnormalities that are not associated with symptoms or clinical manifestations of pancreatitis and decrease to <Grade 4 within 1 week of onset.
 - Isolated Grade 4 electrolyte imbalances/abnormalities that are not associated with clinical sequelae and are corrected with supplementation/appropriate management within 72 hours of their onset.
- Discontinue treatment for persistent Grade 2-3 drug-related AE that do not recover to Grade 0-1 within 12 weeks after last dose except when creatinine, AST, ALT, or total bilirubin were >ULN at baseline.
- Discontinue treatment for any Grade 3-4 drug-related AE that recurs.
- If creatinine >ULN at baseline, withhold treatment for drug-related elevation >1.5 x baseline and resume when ≤ 1.5 x baseline. Discontinue treatment with drug-related elevation >3 x baseline or drug-related elevation that does not recover to ≤ 1.5 x baseline within 12 weeks after last dose.

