6.6. Patient Withdrawal

The reason for a patient's discontinuation from treatment will be documented in the end of study/withdrawal CRF. Patients will be followed for at least 120 days after the last dose of study drug for AEs.

Patients may withdraw from treatment at any time at their own request, or they may be withdrawn at the discretion of the investigator or sponsor for safety or behavioral reasons, or the inability of the patient to comply with the protocol-required schedule of study visits or procedures at a given study site.

Reasons for withdrawal of study treatment may include:

- Objective disease progression;*
- Global deterioration of health status requiring discontinuation;
- Unacceptable toxicity;
- Pregnancy;
- Significant protocol violation;
- Lost to follow-up;
- Patient refused further treatment;
- Study terminated by sponsor;
- Death.

*In the case of radiological progression but in the absence of clinical deterioration, if investigator deems it to be in the patient's best interests, the patient will be allowed to stay on study.

Reasons for withdrawal from study follow-up may include:

- Completed study follow-up;
- Study terminated by sponsor;
- Lost to follow-up;
- Refused further follow-up;
- Death.

If a patient does not return for a scheduled visit, every effort should be made to contact the patient. All attempts to contact the patient and information received during contact attempts must be documented in the patient's medical record. In any circumstance, every effort should be made to document patient outcome, if possible. The investigator should enquire about the reason for withdrawal, request the patient to return for a final visit, if applicable, and follow-up with the patient regarding any unresolved AEs.

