Appendix 8. Management of Immune-related Adverse Events (irAEs)

Gastrointestinal irAEs		
Severity of Diarrhea/Colitis (NCI-CTCAE v4)	Initial Management	Follow-up Management

Grade 1 Diarrhea: <4 stools/day over Baseline Colitis: asymptomatic
	
-Continue study treatment. -Symptomatic treatment (eg, loperamide).
	
-Close monitoring for worsening symptoms. -Educate patient to report worsening immediately. -If worsens: Treat as Grade 2, 3 or 4.

Grade 2 Diarrhea: 4 to 6 stools per day over Baseline; IV fluids indicated <24 hours; not interfering with ADL Colitis: abdominal pain; blood in stool
	
-Withhold study treatment. -Symptomatic treatment.
	
-If improves to Grade ≤1: Resume study treatment. -If persists >5-7 days or recurs: Treat as Grade 3 or 4.

Grade 3 to 4 Diarrhea (Grade 3): ≥7 stools per day over Baseline; incontinence; IV fluids ≥24 h; interfering with ADL Colitis (Grade 3): severe abdominal pain, medical intervention indicated, peritoneal signs Grade 4: life-threatening, perforation
	
-Withhold for Grade 3. -Permanently discontinue study treatment for Grade 4 or recurrent Grade 3. -1.0 to 2.0 mg/kg/day prednisone IV or equivalent. -Add prophylactic antibiotics for opportunistic infections. -Consider lower endoscopy.
	
-If improves: -Continue steroids until Grade ≤1, then taper over at least 1 month; resume study treatment following steroids taper (for initial Grade 3). -If worsens, persists >3 to 5 days, or recurs after improvement: -Add infliximab 5mg/kg (if no contraindication). -Note: infliximab should not be used in cases of perforation or sepsis.

Dermatological irAEs		
Grade of Rash (NCI-CTCAE v4)	Initial Management	Follow-up Management

Grade 1 to 2 Covering \leq30% body surface area
	
 -Continue study treatment. -Symptomatic therapy (for example, antihistamines, topical steroids). 	
 -If persists $>$1 to 2 weeks or recurs: -Withhold study treatment. -Consider skin biopsy. -Consider 0.5-1.0 mg/kg/day prednisone or equivalent. Once improving, taper steroids over at least 1 month, consider prophylactic antibiotics for opportunistic infections, and resume study treatment following steroids taper. -If worsens: Treat as Grade 3 to 4.

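### Protocol Section 7.1.5 ends study participation, where it almost certainly means treatment, after a serious QTcF event, and so contradicts the follow-up rules

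*Protocol*

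**What the plan says.** Protocol Section 7.1.5 first deals with drug. Once QTcF has come down sufficiently, "patients may restart the investigational product at the next lowest dose level". It then names three triggers: no recovery after 2 weeks, QTcF above 515 msec at any time, or symptoms. The consequence is stated as "msec or becomes symptomatic, the patient will be removed from the study".

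Other toxicity rules name treatment as the thing that stops. Section 5.4.3.1 has "Discontinue treatment for any other Grade 4 drug-related AEs or laboratory abnormality", with listed exceptions. Appendix 8, for diarrhea and colitis, has "Permanently discontinue study treatment for Grade 4 or recurrent Grade 3".

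Section 6.6 keeps two lists apart. One opens "Reasons for withdrawal of study treatment may include" and contains unacceptable toxicity. The other opens "Reasons for withdrawal from study follow-up may include" and contains no toxicity reason. The same section says: "Patients will be followed for at least 120 days after the last dose of study drug for AEs".

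The Protocol Summary and Section 3.1 set out what happens to every patient. Treatment may end for unacceptable toxicity, among other reasons. The patient then has a 1-month visit, late immune-related event assessment to 120 days, and telephone survival contact every 8 weeks to the end of the trial.

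**The concern.** Taken at its word, the Section 7.1.5 sentence ends participation because of a toxicity. Everywhere else the protocol keeps following such patients after treatment stops, and none of those passages makes an exception for a QTcF event.

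The patients concerned are selected by a cardiac safety signal, so they are ones whose later course matters for a safety study. A site that followed the sentence literally could drop the post-treatment visits, the scans and the long-term survival calls. It would also affect reporting: SAP Section 6.1 tabulates discontinuation of treatment and discontinuation of study separately, so the wording decides which table the patient enters.

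Acute ECG monitoring is not at issue, because Section 7.1.5 specifies it in detail.

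**Working it through.** The main check is a comparison of texts. The documents state no figure on this point, so there is none to reproduce.

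**1. What literal removal would cut short**

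| Protocol section | Duty after treatment stops | QTcF exception? |
|---|---|---|
| Summary and 3.1 | 1-month visit, assessment to 120 days, survival contact, for all patients | None |
| 6.3 | Visit 28 to 35 days after discontinuation | None |
| 6.4 | Calls at 90 and 120 days after last dose | None |
| 6.5 | Survival contact every 8 weeks to end of trial | None |
| 6.6 | AE follow-up for at least 120 days; survival follow-up even if visits are refused, unless consent is withdrawn | None |
| 7.4 | Scans every 12 weeks unless treatment ended for progression, death or consent withdrawal | None |
| 8.2 | AEs for 28 days or until drug-related toxicity resolves, whichever is later; SAEs to 150 days; either period ends sooner on new anticancer therapy | None |

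**2. Which reading is intended**

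For a treatment stop:
- the sentence just before concerns restarting drug;
- toxicity appears only in the treatment list of Section 6.6 (both lists are open-ended, so this is support rather than proof);
- the End-of-Treatment footnote in all three schedules describes that visit as "conducted at the visit that the patient is discontinued from the trial", yet follow-up comes after it;
- a footnote in Section 6.6 speaks of staying on study when continued treatment is meant.

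For the literal reading:
- Section 7.1.5 uses treatment or investigational product for its other actions and changes noun only here;
- Section 7.1.1, on pregnancy, expressly separates leaving treatment from leaving the study, so the protocol can draw the distinction when it wants to.

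The first group is the stronger. The only precedence clause, in Section 15.2, concerns the protocol against the clinical study agreement and does not bear on this.

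**3. Size**

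Planned arm sizes are from protocol Section 9.3. One patient is 1/70 = 1.43% of the NSCLC arm or 1/30 = 3.33% of the urothelial arm.

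For overall survival, take an extreme case as an upper limit. One patient who would have died before time *t* is instead censored at treatment start, and nobody else is censored. If true survival at *t* is *S*, the Kaplan-Meier estimate becomes *nS*/(*n* − 1), a rise of *S*/(*n* − 1). *S* is not given in the documents; I assume 30% to 70%.

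- *n* = 70: 0.30/69 = 0.43 points; 0.70/69 = 1.01 points.
- *n* = 30: 0.30/29 = 1.03 points; 0.70/29 = 2.41 points.

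Even this overstates the effect. Section 8.2 requires any death within 150 days of the last dose to be reported, whatever treatment came in between, so only a later death could be missed.

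PFS barely moves: SAP Table 9.2.1 already censors toxicity discontinuations at the last tumor assessment.

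**The case against.** The best reply is that this is a slip of the pen with no practical force. The overview lists apply to all patients and treat unacceptable toxicity as one way treatment ends before follow-up begins. Section 6.6 runs AE follow-up from the last dose and asks the investigator to pursue unresolved events and document outcome even on withdrawal. Section 8.2 ties SAE and death reporting to the last dose, not to study membership. A site would have to disregard several explicit instructions to lose the patient. The SAP safety tables (Section 6.2.2) stop at last dose plus 28 days or new anticancer therapy, so most later follow-up would not enter them anyway.

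Most of this stands. It settles what was intended and makes the harm unlikely. It does not make the sentence correct: the rule is mandatory, specific to this event, and says something those passages contradict. The more clearly they require follow-up, the plainer the contradiction. Nor is the 28-day limit a complete answer, since two of the triggers (above 515 msec, or symptoms) can occur at any time, and removal could fall inside that window.

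Two stronger readings are tempting. One is that the protocol deliberately ends follow-up after cardiac toxicity; the surrounding text and the all-patient lists point the other way. The other is that overall survival will be biased because SAP Section 6.3.1 censors at the last visit. That needs a literal misreading, an early event, and a death more than 150 days after the last dose that no one records. The documents do not support presenting it as a likely result.

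**Conclusion.** The wording is wrong as it stands, and the point is minor. A treatment stop is almost certainly meant, but the sentence contradicts the study overview and Sections 6.3 to 6.6, 7.4 and 8.2. What is at risk is individual: visits, scans and long-term survival status in a patient with a cardiac event, and that patient's disposition category.

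The documents give no rate for these events; that few patients would be affected is a judgement. The effect on efficacy estimates is negligible. The survival figures above are ceilings for one patient, under an assumed survival of 30% to 70%, no other censoring and a death that goes unrecorded. Overall survival is a secondary endpoint, Part 2 tests no hypothesis, and no sample size or dose decision changes.

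**What to change.** In protocol Section 7.1.5, replace the closing consequence with: *will be permanently discontinued from study treatment and will continue follow-up per Sections 6.3–6.6, 7.4 and 8.2*. Section 6.6 already provides for withdrawal of consent, so no further exception is needed. Leave the QTcF limits and the monitoring steps unchanged.

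The cost is one phrase in the next protocol amendment. Visits, case report forms and the SAP need no change.
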